**CLINICAL STUDY FLOW CHART****Figure 1: Study Flow Chart**

## SCHE DULE OF EVENTS

Table 1: Schedule of Events

	Visit 1 Day 1 to Day 1	Visit 2 Day 1	Visit 3 Week 2 (± 3 Days)	Visit 4 Week 4 (± 3 Days)	Visit 4a 2 Weeks after touch-up (± 3 Days)	Visit 4b 4 Weeks after touch-up (± 3 Days)	Visits 5-9 Weeks 8-40 after baseline OR touch-up (± 5 Days)	Visit 10 or ET
Screening	Baseline / Tx	Follow-up	Follow-up / Touch-up	Follow-up	Follow-up	Follow-up	Follow-up	Follow-up
PROCEDURE								
Informed consent	X							
Medical history	X	X 						
Demographics	X							
Inclusion/exclusion	X	X 		X 				
Urine pregnancy test 	X	X 	X 	X 				
Treatment or touch-up		X		X 				
MLFS (investigator)	X	X 	X 	X 				
WAS upper perioral lines & oral commissures (investigator if applicable) 	X	X 		X 				
GAIS (subject and investigator)					X	X	X	X
Evaluate device deficiencies		X 		X 				
Photography		X 		X 				
Concomitant meds/procedures	X	X 	X	X 	X	X	X	X
Assessment of AEs	X	X 	X	X 	X	X	X	X

Abbreviations: GAIS, Global Aesthetic Improvement Scale; MLFS, Medicis Lip Fullness Scale; WAS, Wrinkle Assessment Scale

 Omit if the screening and baseline visits occur on Day 1 Prior to treatment Post treatment Omit if touch-up was not performed For females of childbearing potential Optional touch-up at Visit 4 to obtain optimal aesthetic improvement.  
*If a touch-up is performed, a 2wk and 4wk follow-up visits are scheduled (Visits 4a & 4b)* Subjects who are not treated in the upper perioral area or the right & left oral commissures at baseline (i.e. treated in the upper and lower lips only) are not required to have WAS assessed beyond

14(80)

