### 1.5 Risks and Benefits

As the lip appearance is an essential feature in determining the attractiveness of a face, and thus, plays a key role in human social interactions. The primary potential benefit of the study product is a perceived improvement in the visual appearance of lip fullness.

For subjects in the US, another potential benefit is the correction of the upper perioral rhytids, philtral columns and oral commissures.

Injection site reactions (e.g. swelling, erythema, tenderness, pain, bruising, itching, lumps/ bumps, and discoloration) experienced with HA fillers have been observed as consisting mainly of short-term minor or moderate symptoms starting early after treatment that generally resolve spontaneously within one to two weeks after injection. According to published literature, the most common complications related to HA injections in the lips include these injection site reactions.

The most common adverse events (AE) reported in both post-marketing surveillance data and clinical trial data for the *Restylane*® family of products (utilizing the XpresHAn/OBT Technology) injected in the lips are swelling, mass/induration, papules/nodules, pain/tenderness, and bruising/bleeding.

Although most AEs occur within days to weeks following the implant procedure, some AEs, such as swelling and mass, have been reported several weeks to months after the injection. Inflammation, infection, and damage to body structures such as nerves or blood vessels at the injection site, have also been reported. Rare but serious AEs associated with the intravascular injection of soft tissue fillers in the face have been reported and include temporary or permanent vision impairment, blindness, cerebral ischemia or cerebral hemorrhage, leading to stroke, skin necrosis, and damage to underlying facial structures.

Additional information about reported AEs and anticipated risks are included in the product-specific IFU.

To mitigate these risks, only study investigators qualified by education and experience, and who are skilled in the use of dermal fillers from their clinical practice and involvement in clinical research, and with a firm knowledge of the vascular anatomy and understanding of the depth and plane of injection as well as knowledge of the signs and symptoms and management of potential complications will be chosen in order to assure proper device implantation and management of study risk.

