## 3. STUDY DESIGN

### 3.1 Overall Design

This is a prospective, open-label, multi-center study to evaluate the safety and effectiveness of *Restylane Kysse* for lip augmentation and correction of perioral rhytids, if applicable, in subjects with both biological parents of full Chinese descent.

Approximately 50 subjects with a score of 1 (Very Thin) or 2 (Thin) on the MLFS will be enrolled. The upper lip and lower lip scores do not have to be equal as long as each score is either 1 or 2 at baseline.

Following the informed consent and screening process, eligible subjects will be injected in the lips by the investigator at baseline. The method of injection is at the discretion of the investigator and will be recorded. Sufficient amount of product should be injected to achieve optimal aesthetic improvement as determined by the investigator and subject. Optimal aesthetic improvement is defined as at least 1-

point improvement from baseline using the MLFS and the best correction that can be achieved as agreed by the investigator and the subject.

Subjects in the US meeting the WAS inclusion criteria may also receive optional treatment with *Restylane Kysse* in the perioral rhytids at baseline. Treatment of the upper perioral lines, vermillion border, philtral columns, Cupid's bow, and/or oral commissures may be performed to obtain optimal aesthetic improvement, as agreed by the investigator and subject.

Touch-up treatment of the lips and perioral area, if treated at baseline, may be administered 4 weeks after baseline treatment if deemed necessary to obtain optimal aesthetic improvement; this decision should be agreed upon by the investigator and the subject. Touch-up treatment will not be performed if the subject has a disease or condition described in the exclusion criteria or is experiencing an ongoing treatment-related AE that, in the opinion of the investigator, would be worsened by touch-up treatment.

The recommended maximum injected volume per subject per treatment visit is 6 mL (i.e. 1.5 mL for the upper lip, 1.5 mL for the lower lip, and 3 mL for perioral area). Treatment will be performed according to the approved IFU.

Subjects will have in-clinic follow up visits at 2, 4, 8, 16, 24, 32, 40, and 48 weeks after the last injection. If a touch-up is deemed necessary and performed at 4 weeks post-baseline, a second 2-week and 4-week follow-up visits should be scheduled. See flowchart ([Figure 1](#)).

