##### 7.1.1.2 Recording Instructions for Adverse Events

Each subject should be questioned about AEs at each study visit following signing of informed consent, for example, "Since your last clinical visit, have you had any health problems?" Information on AEs can also be obtained from signs and symptoms detected during each examination or from a laboratory test, observations made by the study site personnel, subject diaries, or spontaneous reports from the subjects or their relatives.

Exceptions from AE reporting are normal fluctuations in pre-existing diseases. However, pre-existing illnesses that deteriorate shall be reported as AEs.

When an AE is related to a device deficiency (refer to Section 7.4), including technical device malfunction, the AE shall be recorded on the AE form/module in the eCRF and the technical complaint shall be reported separately on the clinical study complaint form.

Investigators, or other study site personnel, shall record all AEs in the eCRF, including:

- Event term (recorded in standard medical terminology and avoiding abbreviations)
- Affected area
- Start date (first day with symptoms)
- Stop date (last day with symptoms)
- Intensity (mild, moderate, or severe according to definition in Section 7.1.1.2.1)
- Seriousness (serious or not serious, according to definition in Section 7.1.2)
- Causal relationship to study product or study product injection procedure (yes or no)
- Action taken (none, medication treatment, non-pharmacological treatment, or other procedures/tests, subject withdrawn)
- Outcome of the AE (ongoing, recovered, recovered with sequelae, death, chronic/ stable, not recovered at the end of the study)

Each AE will also be assessed for causal relationship and seriousness by the sponsor, in order to fulfill regulatory requirements.

The AE form/module in the eCRF must be signed and dated by the investigator.

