### 9.4 Data Transformations

Responder rate (%) regarding MLFS will be calculated as (number of subjects (or upper/lower lips) with at least one grade improvement from baseline/number of subjects reporting at the specified visit) \*100.

Responder rate (%) regarding WAS will be calculated as (number of subjects (or upper/lower lips) with at least one grade improvement from baseline/number of subjects reporting at the specified visit)\*100.

Responder rate (%) regarding GAIS will be calculated as (number of subjects being at least improved/number of subjects reporting at the specified visit) \*100.

The outcome of the questionnaires regarding FACE-Q will be summarized and transformed to a Rasch score (0-100).

Time to onset of an AE will be derived as the start date minus the date of most recent treatment. If the start date is missing, it will be assumed that the AE started on the day of most recent treatment.

Duration of an AE will be derived as the stop date minus the start date + 1. If the start date is missing, it will be assumed that the AE started on the day of most recent treatment. Missing stop date will not be imputed and therefore no duration will be calculated in these cases. Instead, the number of AEs that were ongoing at the end of the study will be given.

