#### 1.1.1 Study Design

This is a prospective, open-label, multi-center study to evaluate the safety and effectiveness of *Restylane Kysse* for lip augmentation and correction of perioral rhytids, if applicable, in subjects with both biological parents of full Chinese descent.

Approximately 50 subjects with a score of 1 (Very Thin) or 2 (Thin) on the Medicis Lip Fullness Scale (MLFS) will be enrolled. The upper lip and lower lip scores do not have to be equal as long as each score is either 1 or 2 at baseline.

Following the informed consent and screening process, eligible subjects will be injected in the lips by the investigator at baseline. The method of injection is at the discretion of the investigator and will be recorded. Sufficient amount of product should be injected to achieve optimal aesthetic improvement as determined by the investigator and subject. Optimal aesthetic improvement is defined as at least 1-point improvement from baseline using the MLFS and the best correction that can be achieved as agreed by the investigator and the subject.

Subjects in the US meeting the Wrinkle Assessment Scale (WAS) inclusion criteria may also receive optional treatment with *Restylane Kysse* in the perioral rhytids at baseline. Treatment of the upper perioral lines, vermillion border, philtral columns, Cupid’s bow, and/or oral commissures may be performed to obtain optimal aesthetic improvement, as agreed by the investigator and subject.

Touch-up treatment of the lips and perioral area, if treated at baseline, may be administered 4 weeks after baseline treatment if deemed necessary to obtain optimal aesthetic improvement; this decision should be agreed upon by the investigator and the subject. Touch-up treatment will not be performed if the subject has a disease or condition described in the exclusion criteria or is experiencing an ongoing treatment-related AE that, in the opinion of the investigator, would be worsened by touch-up treatment.

The recommended maximum injected volume per subject per treatment visit is 6 mL (i.e. 1.5 mL for the upper lip, 1.5 mL for the lower lip, and 3 mL for perioral area, if treated). Treatment will be performed according to the approved Instructions for Use (IFU).

Subjects will have in-clinic follow up visits at 2, 4, 8, 16, 24, 32, 40, and 48 weeks after the last injection. If a touch-up is deemed necessary and performed at 4 weeks post-baseline, a second 2-week and 4-week follow-up visits should be scheduled.

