#### 2.5.2 Adverse Events (AEs)

All AEs will be coded according to MedDRA and summarized by System Organ Class (SOC), and Preferred Term (PT), including number of subjects with at least one event, associated percentage, and number of events.

For subject counts, a subject will only be counted once per SOC and once per PT in cases where multiple events are reported for a subject within SOC or PT. For event counts, subjects with multiple events in a category will be counted for each event.

The number of subjects with AEs related to study product or study product injection procedure, as well as the number of events, will be presented by SOC, PT, and maximum intensity. Action taken for related AEs will also be summarized by SOC and PT using number of events. Serious AEs will be listed. AEs related to study product or injection procedure with late onset (> 21 days after most recent treatment session) will be listed.

AEs unrelated to study product or injection procedure will be summarized by SOC, PT, and maximum intensity.

For AEs related to study product or study product injection procedure, the number of days to onset and the duration of event will be summarized by SOC and PT using mean, standard deviation, median, minimum, and maximum. Days to onset of an AE will be derived as the start date minus the date of most recent treatment session. Duration of an AE will be derived as the stop date minus the start date + 1.

For the purpose of deriving days to onset and duration, the following date imputation rules will be used.

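### Days to onset and the late-onset listing restart at the touch-up for every area, so a related AE in an area injected only at baseline can be dated about four weeks too early and, if it starts within 21 days of the touch-up, left off the listing

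*SAP*

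**What the plan says.** SAP 2.5.2 defines onset for related AEs as follows: "Days to onset of an AE will be derived as the start date minus the date of most recent treatment session". The result is summarised by SOC and PT. The same section adds one dedicated output for delayed events: "AEs related to study product or injection procedure with late onset (> 21 days after most recent treatment session) will be listed". Protocol 9.4 uses the same origin: "Time to onset of an AE will be derived as the start date minus the date of most recent treatment". None of the three mentions the area injected.

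There can be two sessions. Under Protocol 3.1 a touch-up "may be administered 4 weeks after baseline treatment if deemed necessary to obtain optimal aesthetic improvement". SAP 1.1.1 names its scope: "Touch-up treatment of the lips and perioral area, if treated at baseline, may be administered 4 weeks after baseline treatment if deemed necessary". The Treatment Regimen entry in the protocol synopsis leaves perioral treatment of qualifying US subjects, at baseline and again at Week 4, to the judgement of the investigator and subject.

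Onset of related AEs is a named safety endpoint (Protocol 2.1.1). Protocol 1.5 says of this class of product that "some AEs, such as swelling and mass, have been reported several weeks to months after the injection".

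**The concern.** A delayed reaction is judged by the time since product was placed in the tissue concerned. The SAP measures the time since the subject's latest session, wherever that session's injections went. When the touch-up covers every area treated at baseline, the two measures agree. When it omits one, the clock for that area is reset by an injection it did not receive.

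Take a subject injected in the lips and perioral area on Day 1 and touched up in the lips only at Week 4. A related perioral mass that appears ten days later is reported with an onset of 10 days, although the perioral area was last injected 38 days before. By the SAP's own cut-off this is a late event, and it does not appear on the late-onset listing. The dates are complete and correct, so this is separate from the imputation rules for missing dates.

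At stake are the onset summaries for a named endpoint and the completeness of the only output devoted to delayed reactions.

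**Working it through.** The documents state no figure to reproduce, so the check lists what the rule does to each possible onset day.

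**Inputs**
- Onset origin and cut-off: most recent session, more than 21 days (SAP 2.5.2).
- Touch-up day T, counted from baseline: 4 weeks = 28 days. Table 1 of the protocol heads the column "Visit 4 Week 4 (± 3 Days", giving T = 25 to 31. The heading of Protocol 3.4.4 reads +3 days only, which would give T = 28 to 31.
- AE reporting runs to Week 48 after the last injection (Protocol 7.1.1.1): 48 × 7 = 336 days after T.

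**Formulas**, for an area injected at baseline only, with the AE starting on day d after baseline:
- SAP onset = d if d < T; d − T if d ≥ T.
- Area-based onset = d.
- Listed as late if onset > 21.

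An event is late by area but unlisted under the SAP when d ≥ T and d − T ≤ 21, that is T ≤ d ≤ T + 21. T is at least 25, so every such d exceeds 21.

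| Touch-up day T | Onset days omitted from late-onset listing | SAP onset given | Listed again from day | Onset understated by |
|---|---|---|---|---|
| 25 | 25–46 | 0–21 | 47 | 25 days |
| 28 | 28–49 | 0–21 | 50 | 28 days |
| 31 | 31–52 | 0–21 | 53 | 31 days |

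**Single cases with T = 28**
- Day 26: SAP onset 26, listed, correct.
- Day 28: SAP onset 0, not listed; by area 28.
- Day 38: 38 − 28 = 10, not listed; by area 38.
- Day 49: 49 − 28 = 21, not listed; by area 49.
- Day 50: 50 − 28 = 22, listed, but 28 days too short.
- Day 100: 100 − 28 = 72, listed, but 28 days too short.

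The omission window is 22 days (0 to 21 inclusive) of the 337 calendar days from touch-up to Week 48 (336 + 1), and 22/337 = 6.5%. That is a share of days, not of events.

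**Can a touch-up be partial?** For the perioral area, yes: the synopsis makes Week 4 perioral treatment discretionary. For a single lip, no passage requires both to be re-injected and none says outright that one may be left out.

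**The case against.** The strongest case against runs as follows. The session-based origin is pre-specified and the same in both documents. An AE counts as related if either the product or the injection procedure may have caused it (Protocol 7.1.1.2.2), so a new session close by is a plausible cause. The touch-up step in Protocol 3.4.4 names both lips and, if treated at baseline, the perioral rhytids, and Protocol 5.5.3 says the procedures match those of the first treatment. If every baseline area is re-injected, the error does not arise. Safety is descriptive, and SAP 2.5.2 lists all AEs with dates as collected, so a reader could recompute onset.

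Much of this stands. It is a good reason to keep the session-based value, and it limits the point to partial touch-ups. It does not remove the point: the synopsis allows a lips-only touch-up after perioral treatment, and a general listing does not correct the onset summaries or the late-onset listing.

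A reader might infer more than the documents support:
- That every late reaction in an area not re-injected leaves the late-onset listing. Only those starting within 21 days after the touch-up do.
- That all subjects with two sessions are affected. Only those whose touch-up omitted a baseline area, and who then had a related AE in that area, are.
- That one or two such events would change the reported maximum onset. With follow-up to Week 48, that holds only if no other onset for that PT is longer, and nothing in the documents shows this.

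**Conclusion.** The point holds in a limited form. For an area injected only at baseline in a subject touched up elsewhere:
- a related AE starting 0 to 21 days after the touch-up is reported with that short onset and left off the late-onset listing, although it began 25 to 52 days after the area's only injection (28 to 52 if the +3-day window applies);
- a later one stays listed, with onset understated by 25 to 31 days.

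This rests on partial touch-ups occurring. They are allowed for the perioral area and not excluded for a single lip. No rate is given, so the number of affected events cannot be computed. Incidence, intensity and duration are untouched, and every event remains in the related-AE tables and the general listing. The change is still worth making, because onset is a named endpoint and the protocol itself warns of delayed swelling and mass.

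**What to change.** In SAP 2.5.2:
1. For related AEs, also derive days from the last session, on or before the AE's start, in which the affected area was injected. Use the item "Affected area" from the AE form (Protocol 7.1.1.2) and the treatment record by location (SAP 2.5.1). Where the areas cannot be matched, use the most-recent-session value and flag it.
2. Put an AE on the late-onset listing if it started more than 21 days after the last injection of its affected area, and show days from each session there.
3. Summarise onset by SOC and PT on the area-based value, with the session-based value alongside, so that the fallback does not hide a mixture of origins.

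Note the departure from Protocol 9.4 in SAP 2.8. SAP 2.1 already lets the SAP supersede the protocol's statistical sections, and asks for a SAP amendment if the change precedes database lock.

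Cost: revised wording, a short derivation and a second onset column. An area's last injection is never later than the most recent session, so the listing can only gain events. One thing to check first is whether the eCRF records affected area finely enough to separate upper lip, lower lip and perioral area; the documents do not show this.

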#### Start Date

- If start date is completely missing, it will be assumed that the AE started at baseline.
- If the start date is missing the day, the baseline day will be used provided the imputed date is on or after the subject's first treatment date; otherwise, the day of first treatment will be used.
- If the start date is missing the month, the first treatment month will be used, provided the imputed date is on or after the subject's first treatment date; otherwise, the subsequent month after first treatment will be used.
- If the start date is missing the year, the baseline year will be used provided the imputed date is on or after the subject's first treatment date; otherwise, the subsequent year after first treatment will be used.

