## 2. STUDY OBJECTIVES AND ENDPOINTS

### 2.1 Objectives and Endpoints

#### 2.1.1 Safety Objective and Endpoints

The safety objective of the study is to evaluate the safety of *Restylane Kysse* for lip augmentation in Chinese subjects via assessment of:

- AEs at all study visits.

CCI

CCI

Safety endpoints include:

- Incidence, intensity, duration, and onset of related AEs collected during the entirety of the study.

CCI

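### For the probably few related AEs with an incomplete start date, the SAP 2.5.2 start-date rules can give wrong days to onset and impossible durations, and depart from protocol 9.4 without saying so

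*SAP*

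**What the plan says.** Protocol 2.1.1 names the safety endpoint: "Incidence, intensity, duration, and onset of related AEs collected during the entirety of the study". SAP 2.5.2 summarises days to onset and duration of related AEs by SOC and PT with mean, SD, median, minimum and maximum. Onset is the start date minus the date of the most recent treatment session. For duration: "Duration of an AE will be derived as the stop date minus the start date + 1".

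Where dates are incomplete: "For the purpose of deriving days to onset and duration, the following date imputation rules will be used". Two of the Start Date rules matter here.

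- Day missing: "If the start date is missing the day, the baseline day will be used provided the imputed date is on or after" the first treatment date; failing that, the day of first treatment is used.
- All missing: "If start date is completely missing, it will be assumed that the AE started at baseline".

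Protocol 9.4 has no rule for partial dates. For a missing start it says: "If the start date is missing, it will be assumed that the AE started on the day of most recent treatment".

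SAP 2.1 lets the SAP prevail over the protocol's statistical sections. SAP 2.8 reports no substantial change and does not mention this one.

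**The concern.** The day-missing rule checks the imputed start only against first treatment. Nothing stops it from falling after the recorded stop date, and it takes no account of whether a touch-up came before or after the event. The only explicit start/stop comparison in SAP 2.5.2 is for an end date whose year is missing. A literal application can therefore give a duration of zero or less and an onset that the recorded dates rule out.

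For a completely missing start, SAP and protocol choose different dates once a touch-up has been given, and the reader is not told.

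Onset and duration are named safety endpoints. In a study of about 50 subjects some PT rows may hold few events, so one such AE can move a mean or become the printed minimum. SAP 2.5.2 also plans a late-onset listing: "AEs related to study product or injection procedure with late onset (> 21 days after most recent treatment session) will be listed". If that listing used imputed dates, it could gain rows that do not belong there.

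**Working it through.** The documents give no figure on this point to reproduce. The rules below come from SAP 2.5.2 and protocol 9.4, and the touch-up at about 4 weeks comes from the protocol. Calendar dates, lags and durations are assumptions.

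**What the baseline day means.** The SAP does not define it. The neighbouring rule points to day of the month, because it fills one date part at a time: "If the start date is missing the month, the first treatment month will be used". The year rule is built the same way. If the full baseline date were meant, the check against first treatment could never fail, since both are Day 1. Day of the month is not free of trouble either: the fallback to the day of first treatment is then the same day of the month, so it is circular unless it means the full date.

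**Day missing, no touch-up.** Baseline 25-Mar-2023, start UNK-APR-2023, stop 08-Apr-2023.

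- Day-of-month reading: imputed start 25-Apr. Onset = 25-Apr minus 25-Mar = 31 days. Duration = 8 - 25 + 1 = -16 days.
- Compatible with the record: starts 1 to 8 April, so onset 7 to 14 days and duration 1 to 8 days.
- Baseline-date reading: onset 0 and duration 15 days (25 March to 8 April inclusive). This contradicts the recorded April start.

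**Day missing, with touch-up.** Baseline 20-Mar-2023, touch-up 17-Apr-2023, start UNK-APR, stop 10-Apr. Under the day-of-month reading the imputed start is 20-Apr, onset is 20 - 17 = 3 days and duration is 10 - 20 + 1 = -9 days. The event is credited to a touch-up it had ended before. Compatible values are onset 12 to 21 days and duration 1 to 10 days.

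**Start completely missing, with touch-up.** Same treatment dates, stop 24-Apr.

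- SAP: start 20-Mar, duration 36 days.
- Protocol 9.4: start 17-Apr, duration 24 - 17 + 1 = 8 days.
- The difference is 28 days.
- Onset is 0 under both only if the most recent session means the last one on or before the imputed start. If it means the touch-up, the SAP gives -28.

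Without a touch-up, the two rules agree.

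**Illustrative rates.** These are per day-missing AE under the day-of-month reading, without a touch-up. They enumerate 365 baseline dates in 2023 with every integer lag equally likely; impossible dates such as 31 April are set to the month end.

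| True lag (days) | Imputed onset > 21 days | Duration zero or less, true duration 1-14 / 1-28 / 1-60 days |
|---|---|---|
| 0-7 | 11.5% | 11.5 / 10.3 / 4.8% |
| 0-14 | 23.0% | 23.0 / 17.0 / 7.9% |
| 0-21 | 34.5% | 31.7 / 19.7 / 9.2% |

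The two outcomes overlap, so they are not separate evidence. For lag 0-14, each AE pushed past 21 days has its onset overstated by 14 to 30 days, mean 20.6. One such AE moves a row mean by 20.6/5 = 4.1 days with 5 events, or 20.6/30 = 0.7 days with 30 (assumed row sizes).

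**Earliest compatible date instead.** Same enumeration, no touch-up:

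| True lag (days) | Mean onset error, SAP / earliest | Mean absolute error, SAP / earliest |
|---|---|---|
| 0-14 | about 0 / -5.8 days | 9.5 / 5.8 days |
| 0-21 | about 0 / -7.9 days | 11.1 / 7.9 days |

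**The case against.** The best defence is that this will hardly arise. Daily diaries run for 28 days after each session (SAP 1.5), protocol 7.1.1.2 names diaries as an AE source, clinic visits fall at weeks 2 and 4, and eCRF data are checked and queried (protocol 10.4.1). Day-missing starts are therefore least likely in the very window where the rates were computed. Independent programming and senior review (SAP 2.1.1) should notice a negative minimum duration. This stands as to frequency, but it does not repair the rule: review can flag an impossible value, yet the plan gives no other date to use.

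Second, the negative durations depend on one reading of an undefined term. That is correct, and it limits confidence. The other reading is also wrong, since it discards a recorded month.

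Third, SAP 2.1 allows differences from the protocol. It does. A reader might infer that SAP 2.8 is false, but it denies only substantial changes, and a fallback date rule need not count as one. What can be said is that the change is not disclosed.

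Fourth, the SAP rule is about unbiased for mean onset in the enumeration, while the earliest date runs early. That is a real trade-off. The SAP rule reaches that average through large errors in both directions.

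A reader might also infer that the late-onset listing will contain false rows. The documents do not support that: SAP 2.5.2 ties imputation to deriving onset and duration, shows dates as collected in listings, and does not say which dates select AEs for this one.

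**Conclusion.** The point holds as a minor one, with medium confidence. Under either reading, the day-missing rule can give a wrong onset for a named safety endpoint; under the likelier reading it can also give a duration of zero or less. The rule for a completely missing start departs from protocol 9.4 without mention. That changes results only for a touch-up subject whose AE has a recorded stop date, by about 4 weeks of duration.

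It would be tempting to read the percentages as the share of AE results that will be wrong. They are rates per day-missing AE under assumed lags, durations and calendar dates. The documents give no count of such AEs, so no study-level effect can be stated. Incidence and intensity are unaffected. SAP 2.1.3 is redacted, so a further date rule there cannot be excluded.

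**What to change.** In SAP 2.5.2:

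- **Start completely missing:** restore the protocol 9.4 rule, limited to a treatment on or before any recorded stop date. The limit is needed: with a touch-up on 17 April and a stop on 10 April, imputing the touch-up day would give 10 - 17 + 1 = -6 days.
- **Start day missing:** keep the recorded month and year. Use the earliest compatible date on or after the most recent treatment that fits the known date parts and the stop date. Never impute a start after a recorded stop. The first example then gives start 1-Apr, onset 7, duration 8; the touch-up example gives start 1-Apr, onset 12, duration 10.
- **Most recent session:** define it as the last one on or before the start date used.
- **Late-onset listing:** state that it uses collected dates, or flag imputed ones.
- **Reporting:** give the number of imputed dates, and record the change in SAP 2.8.

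The cost is SAP wording and a little programming, with no new data. The statistical price is that mean onset among imputed AEs is placed early, by about 5.8 days for true lags of 0-14 days and 7.9 days for 0-21, in return for the smaller absolute errors shown above. The CSR should state this direction of error beside the count of imputed dates.
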